12.4 Analysis of Primary Endpoints

The primary endpoint is the rate of CR after 24 cycles of treatment with acalabrutinib, umbralisib, and ublituximab in previously untreated and relapsed CLL patients, assessed per 2018 IW-CLL criteria.¹

Nastoupil et al. reported a CR rate of 44% in previously treated CLL participants who received ibrutinib, umbralisib, and ublituximab.¹⁶ We hypothesize the CR rate will be 44% in **Cohort 1**; given that the depth of response for treatment naïve disease will likely be greater, we hypothesize a CR rate of 50% in **Cohort 2**.

For **Cohort 1**, if 10 or more patients achieve CR by the completion of 24 cycles, we will regard the treatment as efficacious. This sample size provides an $\alpha=0.06$ (false positive type I error) and power $\beta = 91\%$ (one minus false negative type II error) using a one-sided one sample binomial test comparing to a null hypothesis of 20% complete response rate with one BCR inhibitor plus an antibody.

For **Cohort 2**, if 13 or more patients achieve CR by the completion of 24 cycles, we will regard the treatment as efficacious. This sample size provides an $\alpha=0.08$ (false positive type I error) and power $\beta = 82\%$ (one minus false negative type II error) using a one-sided one sample binomial test comparing to a null hypothesis of 30% response rate for one BCR inhibitor plus an antibody.

12.5 Analysis of Secondary and Exploratory Endpoints

The analysis of secondary endpoints will be primarily descriptive, including rate of PR and CRi after 24 cycles of therapy, as well as best achieved rate of PR, CR, and CRi; PFS, time to new therapy (TTNT), and OS (including 2-year, 3-year, and 5-year landmark rates), rate of undetectable MRD in the bone marrow after 6, 12 and 24 cycles, rate of peripheral blood undetectable MRD after 6, 12, and 24 cycles, correlation between undetectable MRD in the

peripheral blood and bone marrow, time to MRD-positive disease recurrence in the peripheral blood, time to clinical disease progression, and safety/tolerability.

A descriptive analysis of rates of therapy discontinuation by cycle 12 will be performed, with subjects grouped by reasons for discontinuation (e.g. achievement of CR, progressive disease, or intolerance). Rates of discontinuation of individual components of the regimen will also be included in this analysis.

The Kaplan Meier method will be used to estimate the median PFS time, PFS, median OS time, TTNT, and OS.

Association between clinical response and established CLL prognostic factors (ZAP70, FISH cytogenetics, *IGHV* mutation status, *TP53* mutation status) will be tested using Fisher's exact test. A similar descriptive analysis will be performed for laboratory correlative studies of BH3 profiling and genomic markers such as *SF3B1*, *NOTCH1*, and *BCR/NFKB* pathway somatic mutations. If feasible, association between clinical response and correlative endpoints will be explored.

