1.3 Secondary Objectives

- Determine the rates of partial remission (PR) and complete remission with incomplete count recovery (CRi) after 24 cycles of therapy.
- Evaluate the median progression-free survival (PFS), time to next treatment (TTNT), and overall survival (OS), as well as the rates at 2 years, 3 years, and 5 years.
- Assess the rates of CR with bone marrow minimal residual disease (MRD)-negativity, peripheral blood MRD-negativity, and correlation between blood and bone marrow MRD-negativity after 6, 12, and 24 cycles of treatment.
- Determine the rate of early therapy discontinuation and time to clinical progression.
- Evaluate the association between established CLL prognostic factors (including *FISH* cytogenetics, somatic mutations and *IGHV* mutation status) and treatment response.
- Confirm the safety and tolerability of the combination.

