2. BACKGROUND

2.1 Study Disease and Rationale

CLL is the most common leukemia in Western countries, with about 19,000 new cases per year in the US. Most patients are over 70 years old at diagnosis, and over 75 when first treated. At this age multiple comorbidities and prescription medications are common, thereby limiting treatment choices in this population and making time-limited oral therapy for CLL appealing.²

CLL patients are divided according to their prognostic factors, and specifically, by the mutation status of the immunoglobulin heavy-chain rearrangement (*IGHV*), chromosomal abnormalities, and specific somatic mutations. Patients with deletion of the short arm of chromosome 17 (del17p) and/or a mutated *TP53* are at the highest risk. They tend to have more steadily progressing disease, a shorter interval before first therapy and a reduced response rate to standard chemoimmunotherapy (CIT).³ Patients with unmutated *IGHV* also have a more rapid progression to therapy than those with mutated *IGHV*, typically with good response but with continuous relapse and reduced durability after chemoimmunotherapy.

Treatment, especially for older patients or those with any of the higher risk markers, is increasingly based on novel targeted therapies, mainly Bruton tyrosine kinase (BTK) and PI3K inhibitors, that usually at least partially overcome these poor prognostic factors. Although most CLL patients respond to these targeted agents, in both the first line and relapsed setting the CR rate is modest (about 10%) and the drugs are given indefinitely.^{4,5} MRD-negativity, which is an independent predictor for survival in CLL after CIT or venetoclax, is seldom achieved with BCR inhibitor monotherapy.⁶ Moreover, each drug has its own unique toxicity profile, in part due to off-target effects.⁷ Ibrutinib, the first FDA approved BTK inhibitor and most widely used targeted small-molecule-agent in CLL, increases bleeding risk (up to 5% high-grade bleeding) and the incidence of atrial fibrillation (up to 16% at 18 months) and hypertension (25% and rising at 36 months).⁸ Idelalisib, a first-generation PI3K δ inhibitor, has a characteristic autoimmune toxicity profile, mainly colitis, hepatitis and pneumonitis.^{5,9}

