4.6 Duration of Follow Up

Participants will be followed for 30 days after removal from protocol therapy or until death, whichever occurs first, for adverse events. Participants removed from protocol therapy for unacceptable adverse event(s) will be followed until resolution or stabilization of the adverse event. Following the 30 day follow up period, participants will be followed for a maximum of 5 years after treatment discontinuation to observe treatment response and survival status.

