10.4 Definitions

Treatment Failure: Responses that should be considered clinically beneficial include CR and PR; all others (e.g., stable disease, non-response, PD, death from any cause) should be rated as a treatment failure.

Overall Survival (OS): Defined as the time from first treatment day to death due to any cause, or censored at date last known alive.

Progression-Free Survival (PFS): Defined as the time from first treatment day to the earlier of progression or death due to any cause. Participants alive without disease progression are censored at date of last disease evaluation.

Event-Free Survival (EFS): Defined as the interval between the first treatment day to the first sign of disease progression or start of a new treatment or withdrawal from the trial because of toxicity or death (whichever occurs first).

Time to Next Treatment (TTNT): Defined as the interval between the first treatment day until the patient starts an alternative therapy for progressive CLL.

Relapse: Defined as evidence of disease progression in a patient who has previously achieved the above criteria of a CR or PR for ≥ 6 months.

Refractory Disease: Defined as treatment failure or as progression within 6 months from the last dose of therapy.

Minimal Residual Disease (MRD)-Negative: Blood or marrow with < 1 CLL cell per 10,000 leukocytes assessed by at least four color flow cytometry (MRD flow), allele-specific oligonucleotide PCR, or high-throughput sequencing using the ClonoSEQ assay.

Complete Remission with incomplete marrow recovery (CRi): Some patients fulfill all the criteria for a CR, but have a persistent anemia, thrombocytopenia or neutropenia apparently unrelated to CLL, but related to drug toxicity. These patients should be considered as a different category of remission, CR with incomplete marrow recovery (CRi). The marrow evaluation should be performed with scrutiny and not show any clonal disease infiltrate.

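### Kaplan-Meier for time to next treatment, with death left out of the definition, would overstate the probability of starting next treatment

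*Combined protocol and SAP*

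**What the plan says.** Section 12.5 names one estimator for three endpoints: "The Kaplan Meier method will be used to estimate the median PFS time, PFS, median OS time, TTNT, and OS".

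Section 10.4 defines those endpoints differently with respect to death:

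- TTNT: "Defined as the interval between the first treatment day until the patient starts an alternative therapy for progressive CLL". Death is not mentioned, and there is no censoring rule.
- PFS: "Defined as the time from first treatment day to the earlier of progression or death due to any cause".
- OS: "Defined as the time from first treatment day to death due to any cause, or censored at date last known alive".

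Event-free survival, in the same section, also counts death. TTNT is therefore the only one of the four that leaves it out.

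Section 1.3 asks for median PFS, TTNT and OS, "as well as the rates at 2 years, 3 years, and 5 years", and section 12.5 repeats those landmark times. Section 4.6 sets the follow-up: "participants will be followed for a maximum of 5 years after treatment discontinuation to observe treatment response and survival status". On status, section 12.5 states: "The analysis of secondary endpoints will be primarily descriptive". Competing risks, cumulative incidence and the handling of a death before next treatment are not mentioned anywhere.

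**The concern.** Under the section 10.4 definition, a participant who dies without further therapy has not had the event. In a Kaplan-Meier analysis that participant can only be censored. Censoring treats the person as still able to start therapy later, at the same rate as those who remain under observation. The curve then describes a setting in which nobody dies first, and its complement is larger than the proportion of participants who in fact go on to another therapy.

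The regimen is time-limited, and section 2.1 offers a long drug-free interval as its possible benefit. TTNT is the endpoint closest to that idea, and deaths in the drug-free interval are the ones handled poorly. The effect makes the regimen look slightly worse on the probability of re-treatment. It grows with follow-up and with the number of deaths in remission.

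**Working it through.** **Plan's own figure.** The plan states no TTNT rate, so there is none to reproduce. The inputs it does give are the definitions above, landmarks at 2, 3 and 5 years, 30 participants per cohort (section 12.2), and one set of outcome figures. Those come from the CLL participants in the umbralisib-ibrutinib study in section 2.5: 2-year OS 95% and 2-year PFS 90%.

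**Direction.** At each next-treatment event both estimators use the same hazard increment, 1 divided by the number at risk. Kaplan-Meier multiplies it by the survivor function for next treatment alone. Aalen-Johansen multiplies it by the probability of being both alive and untreated, which is never larger. One minus Kaplan-Meier therefore cannot fall below the cumulative incidence, and it exceeds it once a death precedes a next-treatment event.

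**Size.** Take constant yearly hazards: l for next treatment, d for death before it.

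- One minus Kaplan-Meier with deaths censored: 1 − exp(−l·t)
- Cumulative incidence: l/(l+d) · (1 − exp(−(l+d)·t))

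Illustrative hazards from section 2.5: d = −ln(0.95)/2 = 0.0256 and l = −ln(0.90)/2 − 0.0256 = 0.0270. This uses progression as a stand-in for next treatment and all deaths as deaths before it, so it shows scale only. The other three rows are assumptions.

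| l, d per year | 3 years: 1−KM vs incidence | 5 years: 1−KM vs incidence | Gap at 3 / 5 years (points) |
|---|---|---|---|
| 0.0270, 0.0256 (section 2.5) | 7.8% vs 7.5% | 12.6% vs 11.9% | 0.3 / 0.8 |
| 0.05, 0.02 (assumed) | 13.9% vs 13.5% | 22.1% vs 21.1% | 0.4 / 1.0 |
| 0.08, 0.03 (assumed) | 21.3% vs 20.4% | 33.0% vs 30.8% | 0.9 / 2.2 |
| 0.12, 0.05 (assumed) | 30.2% vs 28.2% | 45.1% vs 40.4% | 2.0 / 4.7 |

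Gaps are taken before rounding. Worked example, third row at 5 years: 1 − exp(−0.40) = 0.330; (0.08/0.11) · (1 − exp(−0.55)) = 0.727 × 0.423 = 0.308. At 2 years the gap is 0.1 points in the first row and 0.2 to 1.0 in the other three.

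**Against precision.** With 30 participants and no other censoring, the standard error of a proportion p is √(p(1−p)/30). At p = 0.119 this is 5.9 points; at p = 0.404 it is 9.0 points. Pooling both cohorts (60) gives 9.0/√2, about 6.3 points, still above 4.7. In participants, the assumed 5-year gaps are 0.010 × 30 = 0.3 to 0.047 × 30 = 1.4 of 30.

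**Simulation check.** Samples of 30, l = 0.10 per year, 2-year death risk 5%, 4,000 runs, observation closed at 7 years. The 5-year means were 39.7% (one minus Kaplan-Meier) and 37.4% (Aalen-Johansen), with standard deviations of 9.4 and 9.0 points. Kaplan-Meier was higher in 93% of runs and lower in none.

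**The case against.** - **Censoring at death is inferred.** No section writes it down. That is correct, but it is the only handling that keeps the endpoint as defined. Counting death as an event would estimate a different quantity.
- **Kaplan-Meier with deaths censored has a meaning of its own**, as a hypothetical risk in the absence of death. True, but the plan never says it wants that quantity. Landmark rates in a descriptive report will be read as the proportion of participants who were re-treated.
- **The bias is small next to the noise.** This stands in full. It is nonetheless systematic and one-directional, and it can be avoided at no cost in precision.
- **The data may not support the fix.** The long-term follow-up notes in the study calendars mention survival and disease response, not the start of new therapy. For participants in remission, Table 21 stops follow-up 2 years after Cycle 36, where section 4.6 allows 5 years after discontinuation. This deserves attention, but TTNT under any estimator needs the date of next therapy, and OS already needs the date of death. Aalen-Johansen asks for nothing more.
- **An elderly population.** Section 2.1 says of CLL in general: "Most patients are over 70 years old at diagnosis, and over 75 when first treated". A reader might infer many deaths in remission here. The documents do not support that: entry is open from age 18 with performance-status, organ-function and comorbidity limits (sections 2.7 and 2.8), and no age distribution is given for this trial.

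**Conclusion.** The mismatch between section 12.5 and section 10.4 is real, and its direction is certain once a death comes before a later next-treatment event. Its size is not known from the documents: under 1 point at 5 years with the section 2.5 figures, and 1.0 to 4.7 points under the assumed hazards, always below the sampling error. TTNT is secondary and descriptive, so the remission-rate rules, their error rates and the safety trigger are untouched. This is a minor point.

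Two stronger readings are tempting and do not hold. A reader might infer that the same error affects time to clinical progression and time to MRD-positive recurrence. Section 12.5 lists both but names no estimator for either, so neither is an error as written. A reader might also infer that the reported median TTNT will be materially wrong. Under the assumed hazards the Kaplan-Meier median is ln(2)/0.12 = 5.8 to ln(2)/0.05 = 13.9 years, against at most about 6 to 7 years of observation (12 to 24 cycles plus 5 years). The median may often not be reached.

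**What to change.** In section 12.5, take TTNT out of the Kaplan-Meier sentence and state that it will be estimated by Aalen-Johansen cumulative incidence, with death before next treatment as a competing event. Keep Kaplan-Meier for PFS and OS.

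The alternative is to redefine the endpoint in section 10.4 as next treatment or death and keep Kaplan-Meier. That answers a different question. With l = 0.08 and d = 0.03, the 5-year figure becomes 1 − exp(−0.55) = 42.3%, made up of 30.8% re-treated and 11.5% dead without re-treatment, so the name should change with it.

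Either way, give the censoring date for living participants who have not started another therapy. When an estimator is chosen for time to clinical progression and time to MRD-positive recurrence, the same method can be applied.

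The cost is a few lines of text. The analysis needs no item beyond the next-therapy and death dates that TTNT and OS already require; confirm that the follow-up form records the start of next therapy.

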12.6 Reporting and Exclusions

Participants who never initiate protocol therapy will be excluded from all analyses.

12.6.1 Evaluation of Toxicity

All participants will be evaluable for toxicity from the time of their first dose of study medication.

12.6.2 Evaluation of the Primary Efficacy Endpoint

All participants who receive at least one dose of at least one of the study agents will be considered evaluable for the primary efficacy endpoint in an intent-to-treat analysis.

13. PUBLICATION PLAN

The results should be made public within 24 months of reaching the end of the study. The end of the study is the time point at which the last data items are to be reported, or after the outcome data are sufficiently mature for analysis, as defined in the section on Sample Size, Accrual Rate and Study Duration. If a report is planned to be published in a peer-reviewed journal, then that initial release may be an abstract that meets the requirements of the International Committee of Medical Journal Editors. A full report of the outcomes should be made public no later than three (3) years after the end of the study.

APPENDIX A: PERFORMANCE STATUS CRITERIA

ECOG Performance Status Scale		Karnofsky Performance Scale	
Grade	Descriptions	Percent	Description
0	Normal activity. Fully active, able to carry on all pre-disease performance without restriction.	100	Normal, no complaints, no evidence of disease.
		90	Able to carry on normal activity; minor signs or symptoms of disease.
1	Symptoms, but ambulatory. Restricted in physically strenuous activity, but ambulatory and able to carry out work of a light or sedentary nature (e.g., light housework, office work).	80	Normal activity with effort; some signs or symptoms of disease.
		70	Cares for self, unable to carry on normal activity or to do active work.
2	In bed <50% of the time. Ambulatory and capable of all self-care, but unable to carry out any work activities. Up and about more than 50% of waking hours.	60	Requires occasional assistance, but is able to care for most of his/her needs.
		50	Requires considerable assistance and frequent medical care.
3	In bed >50% of the time. Capable of only limited self-care, confined to bed or chair more than 50% of waking hours.	40	Disabled, requires special care and assistance.
		30	Severely disabled, hospitalization indicated. Death not imminent.
4	100% bedridden. Completely disabled. Cannot carry on any self-care. Totally confined to bed or chair.	20	Very sick, hospitalization indicated. Death not imminent.
		10	Moribund, fatal processes progressing rapidly.
5	Dead.	0	Dead.

APPENDIX B: HEPATITIS B SEROLOGIC TEST RESULTS

Interpretation of Hepatitis B Serologic Test Results

Hepatitis B serologic testing involves measurement of several hepatitis B virus (HBV)-specific antigens and antibodies. Different serologic "markers" or combinations of markers are used to identify different phases of HBV infection and to determine whether a patient has acute or chronic HBV infection, is immune to HBV as a result of prior infection or vaccination, or is susceptible to infection.

HBsAg	negative	Susceptible
anti-HBc	negative	
anti-HBs	negative	
HBsAg	negative	Immune due to natural infection
anti-HBc	positive	
anti-HBs	positive	
HBsAg	negative	Immune due to hepatitis B vaccination
anti-HBc	negative	
anti-HBs	positive	
HBsAg	positive	Acutely infected
anti-HBc	positive	
IgM anti-HBc	positive	
anti-HBs	negative	
HBsAg	positive	Chronically infected
anti-HBc	positive	
IgM anti-HBc	negative	
anti-HBs	negative	
HBsAg	negative	Interpretation unclear; four possibilities:
anti-HBc	positive	1. Resolved infection (most common)
anti-HBs	negative	2. False-positive anti-HBc, thus susceptible
		3. "Low level" chronic infection
		4. Resolving acute infection

Adapted from: A Comprehensive Immunization Strategy to Eliminate Transmission of Hepatitis B Virus Infection in the United States: Recommendations of the Advisory Committee on Immunization Practices. Part I: Immunization of Infants, Children, and Adolescents. MMWR 2005;54(No. RR-16).

■ Hepatitis B surface antigen (HBsAg):

A protein on the surface of hepatitis B virus; it can be detected in high levels in serum during acute or chronic hepatitis B virus infection. The presence of HBsAg indicates that the person is infectious. The body normally produces antibodies to HBsAg as part of the normal immune response to infection. HBsAg is the antigen used to make hepatitis B vaccine.

■ Hepatitis B surface antibody (anti-HBs):

The presence of anti-HBs is generally interpreted as indicating recovery and immunity from hepatitis B virus infection. Anti-HBs also develops in a person who has been successfully vaccinated against hepatitis B.

■ Total hepatitis B core antibody (anti-HBc):

Appears at the onset of symptoms in acute hepatitis B and persists for life. The presence of anti-HBc indicates previous or ongoing infection with hepatitis B virus in an undefined time frame.

■ IgM antibody to hepatitis B core antigen (IgM anti-HBc):

Positivity indicates recent infection with hepatitis B virus (<6 mos). Its presence indicates acute infection.

DEPARTMENT OF HEALTH & HUMAN SERVICES
Centers for Disease Control and Prevention
Division of Viral Hepatitis

www.cdc.gov/hepatitis

APPENDIX C: DANA-FARBER/HARVARD CANCER CENTER MULTI-CENTER DATA SAFETY MONITORING PLAN

INTRODUCTION

The Dana-Farber/Harvard Cancer Center Multi-Center Data and Safety Monitoring Plan (DF/HCC DSMP) outlines the procedures for conducting a DF/HCC Multi-Center research protocol. The DF/HCC DSMP serves as a reference for any sites external to DF/HCC that are participating in a DF/HCC clinical trial.

1.1 Purpose

To establish standards that will ensure that a Dana-Farber/Harvard Cancer Center Multi-Center protocol will comply with Federal Regulations, Health Insurance Portability and Accountability Act (HIPAA) requirements and applicable DF/HCC Standard Operating Procedures.

2 GENERAL ROLES AND RESPONSIBILITIES

For DF/HCC Multi-Center Protocols, the following general responsibilities apply, in addition to those outlined in DF/HCC Policies for Sponsor-Investigators:

2.1 External Site

An External Site is an institution that is outside the DF/HCC and DF/PCC consortium that is collaborating with DF/HCC on a protocol where the sponsor is a DF/HCC investigator. The External Site acknowledges the DF/HCC Sponsor as having the ultimate authority and responsibility for the overall conduct of the study.

Each External Site is expected to comply with all applicable DF/HCC requirements stated within this Data and Safety Monitoring Plan and/or the protocol document.

The general responsibilities for each External Site may include but are not limited to:

- Document the delegation of research specific activities to study personnel.
- Commit to the accrual of participants to the protocol.
- Submit protocol and/or amendments to their local IRB. For studies under a single IRB, the Coordinating Center with regulatory documents or source documents as requested.
- Maintain regulatory files as per ICH GCP and federal requirements.
- Provide the Coordinating Center with regulatory documents or source documents as requested.
- Participate in protocol training prior to enrolling participants and throughout the trial as required.
- Update Coordinating Center with research staff changes on a timely basis.

- Register participants through the Coordinating Center prior to beginning research related activities when required by the sponsor.
- Submit Serious Adverse Event (SAE) reports to the Sponsor, Coordinating Center, and IRB of Record as applicable.
- Submit protocol deviations and violations to sponsor, Coordinating Center, and IRB of record as applicable, in accordance with DF/HCC requirements.
- Order, store and dispense investigational agents and/or other protocol mandated drugs per federal guidelines and protocol requirements.
- Participate in any quality assurance activities and meet with monitors or auditors at the conclusion of a visit to review findings.
- Promptly provide follow-up and/or corrective action plans for any monitoring queries or audit findings.
- Notify the sponsor immediately of any regulatory authority inspection of this protocol at the External Site.

